2.4. Sample Size Determination

Up to approximately 200 participants will be enrolled in this study.

The study will randomize approximately 150 participants in a 1:1:1 randomization ratio, resulting in approximately 50 participants in each treatment arm (main study population). In addition, the study will also enroll up to 50 additional nonhospitalized symptomatic participants (in a 1:1:1 randomization ratio) who are immunocompromised with a rebound in COVID-19 within 14 days following completion of an initial 5-day treatment course of nirmatrelvir/ritonavir (population with rebound).

Analyses will be conducted after the main study population is fully enrolled and have completed the Day 44 visit regardless of the number of randomized participants in the population with rebound. There will be 2 analysis time points for reporting the results of this study. The primary analysis will be performed after all participants in the main study population have completed the Day 44 visit. The follow-up analysis will be performed after all participants in the main study population have completed the Week 24 visit. In addition, both analyses (primary and follow-up) will include separate results for the main study population and the additional population with rebound.

As no formal hypothesis testing will be performed for this study, no power calculation was carried out to assess the number of participants required for each treatment arm. For the main study population, the goal of the primary analysis is to estimate the treatment effect for each duration of nirmatrelvir/ritonavir. The smaller numbers of participants in these groups will be reflected in the precision of the estimate of the primary endpoint. Table 2 displays which effect sizes would be excluded based on the expected width of the confidence interval around

DMB02-GSOP-RF02 7.0 Statistical Analysis Plan Template 31-Jan-2022 PFIZER CONFIDENTIAL TMF Doc ID: 98.03 Page 11 of 32 the estimate of the proportion of participants with sustained NP swab SARS-CoV-2 RNA <LLOQ (defined as <2.0 log₁₀ copies/mL) from Day 15 through Day 44 with a sample size of 50.

When the proportion of participants with sustained NP swab SARS-CoV-2 RNA <LLOQ from Day 15 through Day 44 ranges from 0.1 to 0.5, Table 2 displays the precision (width of the confidence interval) for the respective proportion to be estimated with a sample size of 50. That is, the width of the 95% CI does not exceed 14%.

Table 2.Width of 95% CI for the Proportion of Participants with Sustained NP
Swab SARS-CoV-2 RNA <LLOQ	Nirmatrelvir/Ritonavir (n=50)		
Proportion of Participants With Sustained Viral	Width of CI	
RNA level <lloq< th="">	</lloq<>		
0.1	0.083	
0.2	0.111	
0.3	0.127	
0.4	0.136	
0.5	0.139	

3. ENDPOINTS AND BASELINE VARIABLES: DEFINITIONS AND CONVENTIONS

3.1. Primary Endpoint(s)

The primary endpoint, summarized separately for the main study population and the population with rebound, is the proportion of participants with sustained NP swab SARS-CoV-2 RNA <LLOQ (defined as <2.0 log₁₀ copies/mL) from Day 15 through Day 44.

Sustained is defined as NP swab SARS-CoV-2 RNA level not $\geq 2.0 \log_{10}$ copies/mL at any study visit (through Day 44) following the first study visit where the participant's NP swab SARS-CoV-2 RNA <LLOQ.

3.2. Secondary Endpoint(s)

Secondary endpoints include:

- Time to first NP swab SARS-CoV-2 RNA<LLOQ (<2.0 log₁₀ copies/mL) for participants with NP swab SARS-CoV-2 RNA ≥LLOQ at baseline.
- Time to sustained NP swab SARS-CoV-2 RNA <LLOQ (<2.0 log₁₀ copies/mL) through Day 44 for participants with NP swab SARS-CoV-2 RNA ≥LLOQ at baseline.
- Proportion of participants with SARS-CoV-2 RNA <LLOQ in plasma over time.

- Proportion of participants with SARS-CoV-2 RNA level in NP swabs <2.0 log₁₀ copies/mL at each study visit through Day 44.
- Change from baseline in SARS-CoV-2 RNA level in NP swabs and in plasma over time.
- Rebound in SARS-CoV-2 RNA level in NP swabs at follow up (ie, any study visit after end of treatment through Day 44) that is defined as a half (0.5) log₁₀ copies/mL increase or greater in SARS-CoV-2 RNA level relative to end of treatment SARS-CoV-2 RNA level based on treatment regimen, with a follow-up viral RNA level ≥2.5 log₁₀ copies/mL.
- Incidence of TEAEs.
- Incidence of SAEs and AEs leading to discontinuations.
- Proportion of participants with COVID-19-related hospitalization >24 hours, or death from any cause through Day 28.
- Proportion of participants with death (all cause) through Week 24.
- Proportion of participants with COVID-19-related hospitalization of any duration.
- Proportion of participants with COVID-19-related ICU admission of any duration.
- Proportion of participants requiring invasive mechanical ventilation or ECMO.
- Number of days in hospital and ICU stay in participants with COVID-19-related hospitalization.
- Number of COVID-19-related medical visits through Day 44 and through Week 24.
- Duration of each targeted COVID-19 signs/symptoms.
- Proportion of participants with severe signs/symptoms attributed to COVID-19 through Day 44.
- Nirmatrelvir and ritonavir PK in plasma and whole blood (if feasible).

3.3. Other Endpoint(s)

Not applicable for this study.

3.4. Baseline Variables

For viral load data from NP swabs, the baseline window is set up according to study days of Day -2 to Day 1. Only results for samples collected within up to 1 hour post start of dosing will be treated as baseline data. This implies that if there is any issue with the Baseline (Day

DMB02-GSOP-RF02 7.0 Statistical Analysis Plan Template 31-Jan-2022 PFIZER CONFIDENTIAL TMF Doc ID: 98.03 Page 13 of 32 1) measurement (eg, missing, undetectable, taken >1 hour post dose), then the screening measurement, if available, will be utilized as the baseline value. If the screening measurement is not available and the Day 1 measurement is undetectable and taken ≤1 hour post dose, then the baseline will be considered undetectable. If the screening measurement is not available and the Day 1 measurement is missing or taken >1 hour post dose, then the baseline will be considered undetectable. If the screening measurement is not available and the Day 1 measurement is missing or taken >1 hour post dose, then the baseline will be considered missing.

For viral load data from plasma samples, the baseline window will be Day -2 to Day 1, but only results for samples collected within up to 1 hour post start of dosing will be treated as baseline.

For laboratory assessments, COVID-19 signs and symptoms, and vital signs, the baseline window will be Day -2 to Day 1, without any consideration to the time factor.

The following baseline variables will be used in efficacy analysis summarization. See below a list of derived baseline variables:

- eGFR/eCrCl (POC value) categories: Normal (≥90), Mild Impairment (≥60 to <90), Moderate Impairment (≥30 to <60), and Severe Impairment (<30).
- Participants considered immunocompromised based solely on receiving corticosteroids or TNF blockers (yes/no)

3.5. Safety Endpoints

The safety endpoints of this study are:

- Incidence of TEAEs.
- Incidence of SAEs and AEs leading to discontinuations.

Clinical Data Interchange Standards Consortium (CDISC) and Pfizer Standards (CaPS) will be used for the analysis of standard safety data.

3.5.1. Adverse Events

An adverse event (AE) is any untoward medical occurrence in a study participant administered a product or medical device; the event need not necessarily have a causal relationship with the treatment or usage. An adverse event is considered a Treatment-Emergent Adverse Event (TEAE) if the event started on or after the study medication start date. Since time of AE is not collected, AEs that begin on day 1, even if prior to study treatment start, will be considered TEAE.

3.5.2. Laboratory Data

Laboratory data includes hematology, chemistry, and other safety tests. To determine if there are any clinically significant laboratory abnormalities, the hematological and clinical biochemistry and other safety tests will be assessed against the criteria specified in the Pfizer

DMB02-GSOP-RF02 7.0 Statistical Analysis Plan Template 31-Jan-2022 PFIZER CONFIDENTIAL TMF Doc ID: 98.03 Page 14 of 32 reporting standards. This assessment will take into account whether each participant's baseline test results are within or outside the laboratory reference range for a particular laboratory parameter.

3.5.3. Vital Signs

Vital sign measurements, including temperature, pulse rate, respiratory rate, oxygen saturation level, and blood pressure.

4. ANALYSIS SETS (POPULATIONS FOR ANALYSIS)

Data for all participants will be assessed to determine if participants meet the criteria for inclusion in each analysis population prior to unblinding and releasing the database and classifications will be documented per standard operating procedures.

For purposes of analysis, the following analysis sets are defined (excluding participants from Site 1001 from all efficacy analyses):

Participant Analysis Set	Description
Full analysis set (FAS)	All participants randomly assigned to study intervention.
Evaluable analysis set/Safety Analysis Set (SAS)	All participants randomly assigned to study intervention and who take at least 1 dose of study intervention.

The evaluable analysis set will be the primary analysis set for evaluating the primary estimand.

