## 9. STATISTICAL CONSIDERATIONS

Detailed methodology for summary and statistical analyses of the data collected in this study is outlined here and further detailed in the SAP, which will be maintained by the sponsor. The SAP may modify what is outlined in the protocol where appropriate; however, any major modifications of the primary endpoint definitions or their analyses will also be reflected in a protocol amendment.

The efficacy and safety data will be analyzed and summarized separately for the main study population and the additional population with rebound. Further details on the analyses planned for the additional population with rebound will be included in the SAP.

There will be 2 analysis time points for reporting the results of this study. The primary analysis will be performed after all participants in the main study population have completed the Day 44 visit. The follow-up analysis will be performed after all participants in the main study population have completed the Week 24 visit. In addition, both analyses (primary and follow-up) will include separate results for the main study population and the additional population with rebound.

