### 9.2. Analysis Sets

For purposes of analysis, the following analysis sets are defined and will be applied for the main study population and the population with rebound:

Participant Analysis Set	Description
Full analysis set	All participants randomly assigned to study intervention.
Evaluable analysis set/Safety Analysis Set	All participants randomly assigned to study intervention and who take at least 1 dose of study intervention.

The evaluable analysis set will be the primary analysis set for evaluating the primary estimand.

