1. VERSION HISTORY

Table 1.	Summary of Changes
----------	--------------------

Version/ Date	Associated Protocol Amendment	Rationale	Specific Changes
1 28 Apr 2023	Original	N/A	SAP Original Version
2 30 Jun 2023	Original	To add subgroup analysis of primary endpoint by symptoms onset and provide clarification in section 6 of the SAP	 Section 4: Exclude site 1001 from all efficacy analysis. Section 4 was amended to delete the paragraph about multiple enrollers as it is not applicable. Section 6.1.1 was modified to add statistical methodology for primary endpoint. Section 6.1.2: added sensitivity analysis of primary endpoint excluding all participants from site 1030. Section 6.2.16 modified to add censoring method and definition signs and symptoms alleviation/resolution for duration of signs and symptoms endpoint. Section 6.3 modified to add subgroup analysis of primary endpoint. Section 6.3 modified to add subgroup analysis of primary endpoint. Section 6.3 modified to add subgroup analysis of primary endpoint as follows: Duration since first symptom (<= 5 days, > 5 days <=30, >30) Section 6.3 was modified to remove the subgroup analysis of primary endpoint by baseline serology (positive, negative) as it is not applicable in this study.

Version/ Date	Associated Protocol Amendment	Rationale	Specific Changes
			Appendix 1 - Summary of Efficacy Analyses was modified to provide clarification on statistical method.

Table 1.Summary of Changes

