2.1. Modifications to the Analysis Plan Described in the Protocol

Not Applicable.

DMB02-GSOP-RF02 7.0 Statistical Analysis Plan Template 31-Jan-2022 PFIZER CONFIDENTIAL TMF Doc ID: 98.03 Page 7 of 32

Objectives	Endpoints	Estimands
Primary:	Primary:	Primary:
• To describe the effect of nirmatrelvir/ritonavir on viral RNA levels in NP swabs over time for the treatment of COVID-19 in nonhospitalized symptomatic participants ≥12 years of age with COVID-19 who are immunocompromised.	• Proportion of participants with sustained NP swab SARS-CoV-2 RNA <lloq (defined="" <2.0="" as="" log10
copies/mL) from Day 15 through Day 44.</lloq>	• The proportion of participants with sustained NP swab SARS-CoV-2 RNA <lloq (defined="" <2.0="" as="" log10
copies/mL) from Day 15 through Day 44 in nonhospitalized, symptomatic patients ≥12 years of age with COVID-19 who are immunocompromised. This will be estimated without regard to study treatment discontinuation and considering participants receiving non-study antiviral or monoclonal antibody therapy post-baseline for the treatment of COVID-19 as not achieving sustained NP swab SARS-CoV-2 RNA <lloq.< td=""></lloq.<></lloq>
Secondary:	Secondary:	Secondary:
• To describe the effect of nirmatrelvir/ritonavir treatment duration on the rate of sustained virologic clearance in nonhospitalized symptomatic participants ≥12 years of age with COVID-19 who are immunocompromised.	 Time to first NP swab SARS-CoV-2 RNA<lloq (<2.0="" log10 copies/mL) for participants with NP swab SARS-CoV-2 RNA ≥LLOQ at baseline.</lloq> Time to sustained NP swab SARS-CoV-2 RNA <lloq (<2.0 log₁₀ copies/mL) through Day 44 for participants with NP swab SARS-CoV-2 RNA ≥LLOQ at baseline.</lloq 	• Not applicable.

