6.1.2. Sensitivity/Supplementary Analyses

Supplemental analyses will be performed for the primary efficacy endpoint:

- 1. An analysis of the primary endpoint will be conducted excluding data after the date of non-study antiviral or monoclonal antibody start for participants that received non-study antiviral or monoclonal antibody therapy post-baseline (between randomization and Day 44) for the treatment of COVID-19.
- 2. An analysis of the primary endpoint will be conducted to include all NP swab SARS-CoV-2 RNA data regardless of whether participants received non-study antiviral or mAb treatment post-baseline (between randomization and Day 44) for the treatment of COVID-19.
- 3. An analysis of the primary endpoint will be conducted where participants with baseline SARS-CoV-2 RNA level <LLOQ will be excluded.
- 4. An analysis of the primary endpoint will be conducted where participants who do not meet the protocol-defined immunocompromised criteria will be excluded.
- 5. An analysis of the primary endpoint will be conducted excluding participants from site 1030.

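### SAP version 2 drops Site 1001 from every efficacy analysis under an unchanged all-randomized label, with no entry in SAP 2.1 and no analysis that shows the effect

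*SAP*

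**What the plan says.** Protocol 9.2 defines the full analysis set (FAS) as "All participants randomly assigned to study intervention". The evaluable set, which is also the safety set, is the dosed subset of these. Neither definition has a site exception. Protocol section 9 lets the SAP modify the plan where appropriate, but adds that "any major modifications of the primary endpoint definitions or their analyses will also be reflected in a protocol amendment".

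SAP section 4 repeats both definitions and prefaces them with the words "excluding participants from Site 1001 from all efficacy analyses". The version history dates this to version 2 (30 June 2023; version 1 is dated 28 April 2023), where the change reads "Section 4: Exclude site 1001 from all efficacy analysis". The rationale for that version is "To add subgroup analysis of primary endpoint by symptoms onset and provide clarification in section 6 of the SAP", which does not mention Site 1001. Under the heading "2.1. Modifications to the Analysis Plan Described in the Protocol" the entry is "Not Applicable".

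SAP 6.1.1 runs the primary analysis in the evaluable set and the FAS. SAP 6.1.2 lists five supplementary analyses. Two vary the handling of non-study antiviral or antibody therapy, one removes participants below the quantitation limit at baseline, and one removes those who fail the immunocompromised criteria. The fifth reads: "An analysis of the primary endpoint will be conducted excluding participants from site 1030".

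**The concern.** An all-randomized set lets a reader see the result in everyone who entered the randomized comparison. Here the label stays and the content changes. Because the FAS loses the site as well, it cannot serve as a check on the evaluable set.

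The trial is descriptive. With no hypothesis test, the arm proportions and pairwise differences are themselves the result. If Site 1001 participants did better or worse than the rest, those figures differ from the ones that the protocol defines, and nothing planned would show by how much. SAP 2.1, where a reader would look for such a departure, says that there is none.

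**Working it through.** **Which analyses lose the site**
- Primary endpoint: both sets named in SAP 6.1.1 are defined in SAP section 4, so both lose it.
- All-cause death through Week 24: SAP Appendix 1, the summary of efficacy analyses, assigns this endpoint to the FAS. On the wording of section 4, Site 1001 deaths therefore drop out of it.
- Baseline and disposition summaries: SAP 6.4.1 and 6.4.2 use the FAS and are not efficacy analyses, so they can still include the site. One named set then has two denominators.

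**Whether anything restores it**
- None of the five supplementary analyses in SAP 6.1.2 does. The subgroup list in SAP 6.3 does not, and Appendix 1 contains no such row.
- For Site 1030 the plan keeps the site in the main analysis and removes it in a supplementary one. A with-and-without comparison by site is thus already in use in the same SAP version.

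**The plan's own figure, as a yardstick**

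SAP Table 2 reproduces as the half-width 1.96 × √(p(1−p)/50): 0.083, 0.111, 0.127, 0.136 and 0.139 for p = 0.1 to 0.5. On the same basis, at p = 0.5 with 50 per arm, the half-width for a difference between two arms is 1.96 × √(2 × 0.25/50) = 0.196.

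**How far the results could move**

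Inputs: 50 per arm (SAP 2.4). The number at Site 1001 is not given, so k excluded per arm is an assumption, shown from 1 to 10. Let r be the proportion among retained participants and s the proportion at Site 1001.

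- All-randomized arm proportion = [(50 − k)r + ks]/50, so restoring the site shifts the arm by (k/50)(s − r).
- The shift in a difference between arms A and B is (k/50)[(s_A − r_A) − (s_B − r_B)]. It is zero if the gap is the same in both arms and k is equal.
- With r_A = r_B, the extreme is s = 1 in one arm and s = 0 in the other, which gives k/50. If the retained arms differ by d, the extreme is (1 + |d|)k/50.

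With r assumed to be 0.60 in both arms:

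| k per arm of 50 | Range of all-randomized arm proportion | Largest shift in a difference |
|---|---|---|
| 1 | 0.588 to 0.608 | 0.02 |
| 3 | 0.564 to 0.624 | 0.06 |
| 5 | 0.540 to 0.640 | 0.10 |
| 10 | 0.480 to 0.680 | 0.20 |

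These are bounds. As a milder and purely hypothetical case, a 30-point gap between the site and the rest moves an arm by (k/50) × 0.30: 0.018, 0.030 and 0.048 for k = 3, 5 and 8. If the gap is equal in both arms, the difference does not move.

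**The case against.** The strongest reply is that removing a whole site is not a selective exclusion. The rule does not depend on arm, dosing or outcome. If it was decided blind, the arms at the remaining sites stay comparable as randomized, and only the site mix changes. SAP section 4 says that set membership is settled before unblinding, protocol 6.4.3 keeps sponsor staff blinded until the Day 44 visits are complete, and the exclusion appears openly in the version history. All of this stands. A reader might infer that the between-arm comparison is biased, but the documents do not support that.

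Four other stronger readings also go too far:
- **That the exclusion came late in the study.** The documents give the two SAP dates but no enrolment, Day 44 or unblinding dates.
- **That Site 1030 is a second suspect site treated inconsistently.** The SAP gives no reason for the Site 1030 analysis, and the two sites may raise different issues. Site 1030 shows only that the method is available.
- **That the stated precision fails.** Table 2 is a planning figure conditional on 50 per arm, with enrolment approximate. Final numbers are not given, and dropping 5 per arm would take 0.139 only to 0.146.
- **That a protocol amendment was required.** Protocol section 9 asks for one only for major modifications. The endpoint definition is unchanged, and the exclusion of a site of unknown size is not shown to be major.

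Two further points are partly right. Comparing the baseline and efficacy Ns could hint at how many were dropped, but missing endpoint data also reduce the efficacy N (SAP 5.3), and the site's outcomes would stay unseen. If the site's data are unreliable, an analysis that includes them could mislead. That is a reason to label the table, since without it readers cannot tell whether the exclusion mattered.

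**Conclusion.** The point holds as a mismatch between label and content, with a missing disclosure and a missing analysis. The SAP departs from protocol 9.2, and its section 2.1 is wrong to say otherwise. The primary result and the FAS-based mortality endpoint are presented on all-randomized sets that are not all randomized.

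The exclusion may be fully justified, and nothing here argues for reversing it. What is missing is the reason, the count by arm and the timing of this decision relative to unblinding.

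The size of the effect cannot be computed. The k/50 bound assumes equal numbers dropped per arm, 50 per arm in total and equal retained proportions. At an assumed k of 5 the extreme of 0.10 is about half of the 0.196 half-width for a difference. A realistic shift would be smaller and could be nil.

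**What to change.** - Replace the entry in SAP 2.1 with a statement of the Site 1001 exclusion, its reason, its date relative to unblinding, and the number of participants by arm.
- Name the efficacy sets as modified sets excluding Site 1001, so that one name no longer covers two denominators.
- Add one supplementary analysis of the primary endpoint in all randomized and in all dosed participants, including Site 1001. If the reason for exclusion is unreliable data, label the table accordingly.
- Count Site 1001 deaths in the all-cause mortality summary through Week 24, or report them beside it.

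The cost is one supplementary table, a SAP paragraph, some relabelling and a line on mortality. The primary analysis is unchanged.

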5. GENERAL METHODOLOGY AND CONVENTIONS

5.1. Hypotheses and Decision Rules

No formal hypothesis testing will be performed for this study.

5.2. General Methods

All data will be presented by treatment group. Descriptive statistics will be provided for all endpoints.

The number of participants screened, randomized to the double-blind treatment phase, completing the study drug administration, and completing the study will be summarized from the FAS. The reason for all discontinuations will be summarized by treatment group.

Baseline demographic and other characteristics will be tabulated for the FAS and summarized by treatment group. Quantitative variables will be described by standard descriptive statistics (mean, standard deviation, median and range), and qualitative variables will be summarized by frequency tables with number and proportion in each category (with the corresponding sample sizes).

> DMB02-GSOP-RF02 7.0 Statistical Analysis Plan Template 31-Jan-2022 PFIZER CONFIDENTIAL TMF Doc ID: 98.03 Page 15 of 32

